Intergenerational transmission of sucralose and acesulfame-potassium from mothers
to their infants via human milk: a pharmacokinetic study

NCT05379270

DATE: April 9th, 2024

RESEARCH PROTOCOL

TITLE: Intergenerational Transmission of Low-calorie Sweeteners in Breast Milk

RESEARCH PLAN

A. Specific Aims

Aim 1: Determine the pharmacokinetics of sucralose and ace-K in mothers' breast milk and plasma after ingestion of a commercially-available diet beverage containing sucralose and ace-K.

Hypothesis 1: We hypothesize that ace-K will be rapidly transferred into breast milk, with peak concentrations measured within 1 hour of diet soda ingestion. We further hypothesize that sucralose will appear in the breast milk approximately 2 hours after ingestion, with peak concentrations detected approximately 8 hours later.

Aim 2: Assess the pharmacokinetics of sucralose and ace-K in exclusively breastfeeding infants following maternal ingestion of commercially-available diet beverage containing sucralose and ace-K.

Hypothesis 2: We hypothesize that sucralose and ace-K concentrations in infants' plasma will be proportional to concentrations measured in their mothers' breast milk.

B. Background and Significance

Low-calorie sweeteners (LCS), including sucralose and acesulfame-potassium (ace-K), provide sweetness without calories, and beverages with LCS are consumed by 44% of lactating women in the United States. The number of consumer products containing LCS has increased four-fold in recent years, and this trend will likely continue with ongoing public health efforts to reduce added sugars. Due to their chemical and physical properties, sucralose and ace-K are found widely in foods and beverages, often in combination. Yet, most consumers are unaware of their presence in a diverse array of products (e.g. non-diet fruit drinks, such as Hawaiian Punch™, no sugar added ice cream, "high-fiber" oatmeal, Carb Smart bread™) in addition to diet beverages. Neither sucralose nor ace-K are metabolized;³ and thus, both are detectable in biological fluids, including human breast milk. However, the current understanding of LCS effects on diet, weight, and health, especially when exposure begins early in life, is extremely limited.

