[name]., C.N.M, co-investigator, is an Assistant Professor in the GW School of Nursing and has extensive experience recruiting and enrolling women in biomedical research studies. [name] is also a clinical midwife at the GW Midwifery Practice within the Department of Obstetrics and Gynecology at the GW School of Medicine and Health Sciences, and has regular contact with a large volume of breastfeeding mothers.

[name] and [name] have recently collaborated on an analysis of low-calorie sweetener intake among lactating women using data collected from 1,422 lactating women in the Infant Feeding Practices Study II (IFPSII). In this sample, 44% of lactating mothers reported consumption of LCS-containing beverages in 2005-2007, 18% of whom reported consumption once per day. A manuscript reporting these findings has been submitted and is currently under review:

1. Huang Q, **Murphy J, Smith ER, [name].** Diet beverage intake during lactation and associations with maternal and infant outcomes in the Infant Feeding Practices II Study [under review, *Journal of Pediatric Gastroenterology and Nutrition*].

D. Research Design and Methods

Mother-infant dyads will be recruited from the GW Midwifery Service, a division within the GW School of Medicine and Health Sciences (GWSMHS). Eligibility will be assessed during a phone screening, after which, eligible mothers will schedule a Zoom enrollment visit, and will subsequently be scheduled for a study visit approximately one week later, which will be 9 hours in duration.

During the enrollment visit (remote via Zoom), participants will provide electronic consent, after which demographic data will be collected, and mothers will be provided with instructions for completing an online, photo-assisted, 7-day food record for 7 days prior to their in-person study visit. At the end of the Zoom™ visit, the in-person visit, to take place at Children's National Hospital, will be scheduled for approximately one week later.

During the week prior to their scheduled study visit, mothers will be instructed to avoid all products containing low-calorie sweeteners (and will be given a list of specific products to avoid) and to complete an online, photo-assisted, 7-day food record.

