After ingestion of the diet beverage, mothers will remain at the CRU for eight hours and will provide a plasma sample 0.5, 1, 1.5, 2, 3, 4, 6, 8 hours (6 mL at each timepoint) following diet beverage ingestion and a breast milk sample 1, 2, 3, 4, 6, 8, 12 hours following diet beverage ingestion (10 mL at each timepoint).

A plasma sample (100 μ L) will be collected from each infant at one of the following prespecified time intervals following maternal ingestion of the LCS containing beverage: 1.5-3 hours, 3-5 hours, 5-7 hours, 7-9 hours, and 9-14 hours. The infant sampling approach is designed to capture the timeframes when maternal breast milk concentrations for ace-K and sucralose will be at their maximum levels, while collecting only a single plasma sample from each infant to minimize risk. Infants' plasma will be collected via heel stick to reduce pain and minimize risk. Heel sticks are the most common way to collect infants' blood and are appropriate for most babies, including premature infants, neonates, and babies <6 months old. Heel sampling will be conducted by trained nursing staff in the CRU.

Breast milk samples will be immediately frozen at -20°C and transferred to a -80°C freezer at the end of each visit for long-term storage. Blood samples will be centrifuged at 4°C and the plasma stored at -80°C until analysis.

After collection of plasma and breast milk samples at the 8-hour timepoint (described above) mother-infant dyads will return home. The mother will be asked to collect the 12-hour breast milk sample at home and bring it to the hospital the following day. Additionally, the mother will be asked to complete a 3-day online, photo-assisted food record for the next three days and to continue to avoid products with LCS. The mother will be asked to return to the clinic between 7AM-9AM on these following three consecutive days (24, 48, and 72 hours after diet beverage ingestion) to provide a blood sample (6 mL each day) by a venous blood draw by a trained phlebotomist and to provide a breast milk sample (10 mL, 24-hour time point only). The total amount of blood collected from mothers over the course of the study (9-hour long study visit, and sample on three consecutive days) will be 72 mL. The total amount of breast milk collected from mothers over the course of the study (9-hour long study visit and 24-hour sample) will be 90 mL. The infant will provide a single blood sample, for a total of 100 μ L collected over the course of the study.

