E. Study Population:

We plan to study 50 lactating mothers and their infants, for a total of 100 participants. Eligibility will be assessed during a phone screening. For eligibility, mothers will have given birth within the past 6 months, be ≥ 18 years of age, and be exclusively breastfeeding. We will limit enrollment to mothers of infants <6 months of age, consistent with recommendations to introduce solid foods. Any individual with a known allergy or contraindication to LCS will be excluded. Only mothers whose infants are ≥ 4 weeks

corrected age will be eligible. Any mothers or infants with an active nutritional disorder known to cause malabsorption will be excluded.

Planned distribution by sex: We will recruit lactating women and their infants. All mothers (n=50) will therefore be female. However, we will recruit infants irrespective of their sex and therefore anticipate that approximately half (n=25) of the total sample of infants (n=50) will consist of females and half (n=25) will consist of males.

- Rationale: This research topic pertains specifically to lactating women because this study aims to measure low-calorie sweetener concentrations in the breast milk. However, findings will pertain to both males and female infants and therefore both boys and girls will be included

Planned distribution by race/ethnicity: Mother-infant dyads will be recruited without bias to race or ethnicity, and eligibility for inclusion within the study will not be determined by these factors. We anticipate the demographic profile of participants will be proportional to the race/ethnic distribution of mothers seen at The GW Midwifery Service.

F. Human Subjects

All of the data collected in this study are collected specifically for research purposes. Data will be provided through self-report of the mother (demographic information, habitual lowcalorie sweetener consumption, infant anthropometry etc.) and collected of biospecimens, including blood and breast milk, as well as measurement of maternal height and weight in the Clinical Research Unit.

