1. Participant recruitment: Mother-infant dyads will be recruited from the waiting room of the GW Midwifery Service, a division within the GW School of Medicine and Health Sciences, where co-investigator [name] is a practicing nurse midwife. We will also recruit using provider referral (from providers at GW Midwifery Clinic, including [name]), word of mouth, social media, and through circulating recruitment flyers and study information via local community organization list-serves.
2. Consent process: Mothers will attend a private webinar (approximately 30 minutes, held via Zoom with a research team member, parent, and their child), during which electronic informed consent will be obtained. Electronic consent will be obtained because this first study visit will take place entirely online (via Zoom). A study team member will explain the study to the mother and will first go over the electronic consent form with them. Mothers will be asked to read and review the consent form. All mothers will receive a verbal lay explanation of the purposes, procedures, and potential risks of the study and of their rights as research participants. Mothers will be given the opportunity to discuss the study with their friends and family members prior to agreeing to participate. The parent will be reminded that they may withdraw consent at any time throughout the course of the study. The mother will have the opportunity to ask any questions before electronically signing the form. Written consent will then be obtained at the start of the

in-person study visit, approximately one week later, prior to beginning any of the in-person study procedures such as collection of breast milk and blood samples.

3. Compensation provided: Compensation of up to \$400 will be provided. This includes \$25 for completion of the Zoom visit, \$25 for completion of the photo-assisted food records, \$200 for the 9-hour in-person study visit, and \$50 per sample obtained at 24, 48, and 72 hours (three consecutive mornings after study visit). Additional compensation will be provided to cover the cost of transportation to/from study and/or parking on each day of the study (9 hour visit and sample collection on three subsequent days). Participants will also be provided with a small study branded gift bag (estimated \$30 value) containing a small handheld breast pump, cooler bag, and a onesie for the infant.

G. Risks and Side Effects:

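### Aim 2 ties each infant's single plasma value to the mother's post-drink milk, but the plan neither ensures nor records that the infant was fed that milk before the heel stick

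*Protocol*

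**What the plan says.** **Target.** In Protocol section A, Aim 2 reads "Assess the pharmacokinetics of sucralose and ace-K in exclusively breastfeeding infants following maternal ingestion". Hypothesis 2 expects that "concentrations in infants' plasma will be proportional to concentrations measured in their mothers' breast milk".

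**Infant sampling.** Section D times the heel stick from the mother's drink, not from a feed. A 100 μL sample "will be collected from each infant at one of the following prespecified time intervals following maternal ingestion of the LCS containing beverage", with five windows running from 1.5 to 14 hours. "The infant will provide a single blood sample", and no infant baseline is planned.

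**Feeding.** Section E requires mothers to have given birth recently "and be exclusively breastfeeding". The term is not defined, and expressed or stored milk is not mentioned. The only feeding item in section D is how long ago the last feed was. It is asked with the medical-history questions at the start of the visit, before the drink.

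**Avoidance and baseline.** In the week before the visit, "mothers will be instructed to avoid all products containing low-calorie sweeteners". A baseline milk sample is taken from the mother before the drink.

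**Analysis.** SAP section 4.3 (Planned Analyses) models the sparse infant samples together with the maternal data and says that further infant covariates will be examined. The SAP text available names no feeding input and no sensitivity analysis based on what the infant was fed.

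**The concern.** The step from maternal milk to infant plasma passes through what the infant swallowed, and the plan collects nothing on that step after the drink. An exclusively breastfed infant can be given milk expressed earlier.

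- Milk expressed before the drink contains none of the study dose. The infant would look as if little or nothing had been transferred.
- Milk expressed before the avoidance week could contain sweetener from the mother's usual diet. The avoidance instruction governs what she consumes that week, not the age of the milk in a bottle. The baseline sample does not test stored milk.

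In either case the infant would be paired with milk it did not drink. The error could not be found or repaired after collection. At stake are the infant concentration curve and the milk-to-infant relation in Aim 2. Maternal pharmacokinetics (Aim 1) are not affected.

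**Working it through.** The plan states no figure on this point, so there is none to reproduce. The first step is textual; the others show scale under stated assumptions.

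**1. What is fixed and what is left open.** Fixed: the time of the drink, the mother's milk sampling times, and the infant's window. Left open: whether the infant fed between the drink and the heel stick, when, on which milk, and how much. Hypothesis 2 needs all of these.

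**2. Samples affected.** Inputs: 40 completing dyads (SAP 4.3, Sample Size) and five windows (Protocol D). Equal allocation to windows is my assumption, giving 40/5 = 8 infants per window. Let f be the share of infants who had only pre-drink milk before the heel stick. The documents do not give f; I take 5% to 30%.

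- Expected samples affected = 40 × f
- Chance that a window of 8 holds at least one = 1 − (1 − f)^8
- Mean slope relative to its true value, if those infants read zero and f is unrelated to milk concentration = 1 − f

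| f | Affected of 40 | At least one in a window of 8 | Relative slope |
|---|---|---|---|
| 5% | 2 | 34% | 0.95 |
| 10% | 4 | 57% | 0.90 |
| 20% | 8 | 83% | 0.80 |
| 30% | 12 | 94% | 0.70 |

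A simulation with log-normal milk and infant values (log SD 0.5 for milk, 0.4 for the infant given milk, both assumed) gave relative slopes of 0.949, 0.901, 0.799 and 0.702, in line with 1 − f. With the protocol's 50 dyads (10 per window) the affected count is 2.5 to 15, and the chance of at least one per window is 40% to 97%.

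**3. Why no single loss per window can be given.** Hypothesis 1 has ace-K peaking in milk within 1 hour, and sucralose appearing only at about 2 hours and peaking about 8 hours later. A pre-drink bottle at 1 hour would therefore remove almost no sucralose, but possibly most of the ace-K available to an early sample. Feed timing matters too. If feeds come every 2.5–3 hours (assumed), the first window allows 1.5/3 = 0.5 to 3/2.5 = 1.2 feeds. Some infants there would have had no post-drink feed of any kind, and would read low whatever milk is used.

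**4. Older milk.** Protocol section C reports LCS beverage use by 44% of lactating women, 18% of whom used them once per day: 0.44 × 0.18 ≈ 0.08. Suppose 20% of infants get a bottle and half of those bottles predate avoidance (both assumed). Then 40 × 0.20 × 0.5 × (0.08 to 0.44) ≈ 0.3 to 1.8 infants. The use figures are for beverages only and date from 2005–2007, so this is only a guide.

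**The case against.** The strongest objection is that the frequency is conjecture. Mothers stay at the research unit for 8 hours and the dyad goes home together, which implies that the infant is present and can be fed at the breast. The gift bag "containing a small handheld breast pump, cooler bag, and a onesie for the infant" (Protocol section F, compensation) is weak evidence of bottle feeding: no time of handover is given, and those items also serve the 12-hour sample collected at home. This stands for most of the windows. It is weaker for the 9–14 hour window, because the dyad leaves after the 8-hour samples and later feeds are unobserved. Even on site, feeding at the breast is neither requested nor recorded.

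A second objection is that this is only a missing feed log. That is largely right, provided the log includes the source of the milk. Times and volumes alone would pair a stored bottle with milk sampled at that hour.

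A third is that the infant input in the model may yet be specified; one part of the SAP was not available to check. That also stands, but no model specification can recover feeding data that the protocol does not collect.

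A reader might infer more than the documents support:

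- That the plan expressly permits stored milk. It is silent.
- That one earlier bottle removes a fixed share of intake equal to one over the number of feeds. Hypothesis 1 rules this out, because the two sweeteners enter milk on different schedules.
- That old milk matters as much as pre-drink milk. It needs several unlikely conditions to hold together.

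**Conclusion.** The gap is real and should be closed, because the error cannot be detected or repaired once the single sample has been taken. Its size is unknown. The figure of 2–12 affected samples of 40, with a matching 5–30% fall in the mean plasma-to-milk slope, rests on an assumed share and on affected infants reading zero. The true share is probably low while dyads are supervised. Contamination from milk that predates avoidance is possible but remote. The documents do not support concluding that Aim 2 will be invalid, only that it lacks a link that is cheap to supply.

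**What to change.** 1. In the visit instructions, ask mothers, where feasible and without restricting feeding, to feed at the breast or with milk expressed after the drink until the heel stick.
2. For each feed from the drink to the heel stick, record its time, its source (breast, or expressed with date and time of expression) and its approximate volume.
3. State in the SAP that this record is the infant input to the population PK model. Enter pre-drink milk expressed during avoidance at the mother's measured baseline milk concentration, an approximation that should be stated. Enter older milk at the concentration of an aliquot, if one was kept.
4. Keep every infant with a known input in the primary fit. Add a sensitivity analysis excluding infants with no post-drink milk feed or with a feed of unknown concentration.

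The cost is a short feed record, an occasional extra milk aliquot and a few sentences in the protocol and SAP.

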We have previously demonstrated that sucralose and ace-K are present in human breast milk and are ingested by nursing infants. Sucralose and ace-K have undergone extensive safety evaluations and are approved by the US Food and Drug Administration (FDA) as food additives and by numerous other regulatory bodies worldwide. While their safety is well-established from a toxicological perspective, sucralose and ace-K elicit striking metabolic effects, and accumulating epidemiologic

and mechanistic evidence demonstrates that early life LCS exposure may adversely impact future cardiometabolic disease risk.

Given that early exposures impact later development of cardiometabolic disease, sucralose and ace-K exposure via the breast milk may adversely impact developmental programming of cardiometabolic risk, through mechanisms including potential alteration of infants' taste preferences, appetite, and/or gut microbiome composition. The purpose of this study is to measure sucralose and ace-K in maternal breast milk and plasma at pre-specified, serial, time-points for 72 hours, as well as in a sample of infants' plasma. This will serve as a critical step towards our long-term goal of elucidating effects of early life LCS exposure on infants' future diet, weight, and health.

C. Preliminary Studies

The PI is [name] Ph.D., an Assistant Professor in the Department of Exercise and Nutrition Sciences at the George Washington University (GW). [name] is a nutrition scientist with a research focus on the role of LCS in diet, weight, and cardiometabolic health. [name] has nearly ten years of experience studying LCS and over five years of experience studying LCS exposure via breast milk. [name] has led and/or contributed to two prior studies involving human breast milk collection, referenced below:

1. **[name], Gardner AL, Bauman V, Blau JE, Garraffo HM, Walter PJ & Rother KI.** Nonnutritive sweeteners in breast milk. *Journal of Toxicology and Environmental Health A*. 2015; 78 (16): 1029-32.
2. **Rother KI, [name], Walter PJ, Garraffo HM, Demarath EW, Fields DA.** Pharmacokinetics of Sucralose and Acesulfame-potassium in Breast Milk Following Ingestion of Diet Soda. *J Pediatr Gastroenterol* 2018 Mar;66(3):466-470. PMID: 29077645

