- The study procedures and the potential risks associated with each are described below.
 - General: study participation requires compliance with study procedures for up to 4 days. Some individuals may find the time required to complete the study procedures to be an inconvenience in their routine life.
 - We do not anticipate any long-term risks to participants from participation in this study. However, there is always the possibility of risks currently unknown and the potential breach of privacy.
 - To minimize the risk of breach of confidentiality, all data will be immediately de-identified following collection. Data will initially be associated with an alphanumeric code and a copy of the key to this code will be kept in a locked filing cabinet. All computers used for analysis of this data are password protected and kept in locked offices and/or laboratories.
 - Blood Draws: Although blood draws are a standard medical procedure, there is a risk of discomfort at the site of the needle entry or bruising at the site. There is also a remote risk of fainting or local infection associated with drawing blood.
 - To minimize risk associated with blood draws, only trained phlebotomy staff in the Clinical Research Unit at Children's National, will carry out these procedures. Furthermore, we will collect blood samples from infants via heel stick to minimize pain and reduce the invasiveness of the procedure.
- Mothers will be made aware that study participation is entirely voluntary and will have the opportunity to choose not to participate. Mothers and their infant will have the opportunity to drop out of the study at any time.

Our assessment of risk does not preclude the potential for unanticipated adverse events, serious or otherwise, since it is not always possible to predict with certainty the absolute risk involved for any given individual. Therefore, we plan to monitor the data and the safety of the study as follows:

- An adverse event (AE) is any untoward medical occurrence in a subject undergoing a study-related procedure and believed reasonably to be caused by a study-related procedure. An adverse event in our study could involve a sign, symptom, abnormal laboratory value or vital sign, and any combination of these.
- Each mother-infant dyad will be evaluated for adverse events through examination a continued telephone contact with participants throughout the entire study.

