- The possibility of adverse events will be monitored for each mother and infant and will be attributed to the study procedures/design by the PI and collaborator [name] [name] MD (who is a neonatologist and pediatric pharmacologist at Children's National Hospital, please see letter enclosed), according to the following categories:
 - a. Definite: Adverse event(s) will clearly be related to the intervention or study procedures.
 - b. Probable: Adverse event(s) will likely be related to the intervention or study procedures.
 - c. Possible: Adverse event(s) may be related to the intervention or study procedures.
 - d. Unlikely: Adverse event(s) will doubtfully be related to the intervention or study procedures.
 - e. Unrelated: Adverse event(s) will clearly not be related to the intervention or study procedures.
 -
- The following scale will be used in grading the severity of any adverse events noted during this study:
 - 1 No adverse event or within normal limits
 - 2 Mild adverse event
 - 3 Moderate adverse event
 - 4 Severe adverse event resulting in hospitalization or prolongation of existing hospitalization, a persistent or significant disability/incapacity, or a congenital anomaly/birth defect
 - 5 Life-threatening or disabling adverse event
 - 6 Fatal adverse event.

Serious unanticipated events will be reported within 24 hours to the IRB at GW and at CNH. Adverse events will be considered serious if graded 3 or higher on the scale outlined above. An adverse event report including a description of the event, when the event occurred, and when and how the event was reported, will be generated for each event. Any documentation related to the event, or its attribution will be included in the report.

The PI ([name]) will conduct a review of adverse events upon completion of every mother-infant dyad. She will evaluate the frequency and severity of the adverse event(s) and, in conjunction with [name] [name] and the IRB, will determine if modifications to the protocol or consent forms are required. A report to the IRB will be made at a minimum of once every 6 months, including when re-approval for the protocol is sought.

H. Benefits:

There are no direct benefits associated with participation in this study. However, the potential public health benefits of this study are of substantial magnitude. The consumption of LCS is widespread, including among lactating women, yet effects of early life LCS exposure are not well understood.

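### The adverse event definition requires a suspected link to a study procedure, but the attribution scale also covers the intervention and unrelated events, so events not suspected at first need not be recorded

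*Protocol*

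**What the plan says.** All the safety rules are in Protocol Section G (Risks and Side Effects).

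- **Definition.** An adverse event is "any untoward medical occurrence in a subject undergoing a study-related procedure and believed reasonably to be caused by a study-related procedure". The two conditions are joined: the person is undergoing a study procedure, and a study procedure is reasonably believed to be the cause.
- **Attribution.** Events "will be attributed to the study procedures/design by the PI and collaborator", who is a neonatologist and pediatric pharmacologist. The scale has five levels: Definite, Probable, Possible, Unlikely and Unrelated. Each level refers to the intervention as well as to study procedures, for example "Unrelated: Adverse event(s) will clearly not be related to the intervention or study procedures".
- **Grading.** "The following scale will be used in grading the severity of any adverse events noted during this study".
- **Reporting and review.** A report is written for each event. The principal investigator reviews the frequency and severity of adverse events when each dyad completes. Events graded 3 (moderate) or higher count as serious, and those that are both serious and unanticipated go to the two IRBs within 24 hours.
- **Surveillance.** Each dyad is evaluated for adverse events by examination and by telephone contact for the whole study.

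**The concern.** The definition decides which events enter the safety record, and the scale decides how the recorded events are classified. If a belief about cause is needed before an event counts, the causality judgment has in effect been made before the two named assessors see the event. The scale applies only to adverse events, so it cannot bring back one that never met the definition.

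This sits badly with the section's stated reason for monitoring, which is that unanticipated events are possible and some risks may be unknown. An unknown risk is the kind least likely to be suspected when it first appears. Events that look incidental one at a time would be available to the review after each dyad only if someone had recorded them.

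The second part of the concern is exposure. Section B names milk as the route of interest: "sucralose and ace-K exposure via the breast milk may adversely impact developmental programming of cardiometabolic risk". The definition names neither the beverage nor milk exposure, while the attribution scale does name the intervention.

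**Working it through.** No arithmetic applies. The check is to set the passages side by side and follow three kinds of event through them.

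**Inputs.** The definition, attribution scale, grading rule, reporting rule and review rule in Protocol Section G; the use of the word procedure in Sections F, G and O.

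1. **An event suspected at first and later judged unrelated.** It meets the definition, is recorded, and can be placed under Unlikely or Unrelated. Definition and scale agree. The two lowest categories therefore need not be empty under the definition.

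2. **An event not suspected at first.** It fails the second condition of the definition. The scale has a place for it (Unlikely or Unrelated), but the scale is applied to adverse events, and this is not one as defined. Grading, the event report and the review after each dyad all use the same term, so each inherits the restriction. No other rule in the documents supplied requires recording regardless of suspected cause. Definition and scale disagree here, however broadly procedure is read.

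3. **An event suspected to come from the beverage, or from sweetener in milk.** The scale covers it as related to the intervention. Whether the definition covers it depends on what counts as a procedure.
   - *For a narrow reading:* the scale names the intervention separately from study procedures. Section G announces "The study procedures and the potential risks associated with each are described below", and the only physical procedure it then describes is blood sampling, including the infant heel stick. Section F (consent process) takes its examples from sampling: "prior to beginning any of the in-person study procedures such as collection of breast milk and blood samples".
   - *For a broad reading:* the Section F examples are not exhaustive. Section G's risk list also leaves out milk collection, which Section F calls a study procedure, so absence from that list proves little. Section G speaks of complying with procedures for up to 4 days, and Section O says some procedures take place over Zoom, so the word reaches beyond sampling. The lead-in to the scale refers to procedures/design, which suggests loose usage. The definition also does not require that the causal procedure be performed on the person who has the event.
   - *Result:* the text does not settle the matter.

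Step 2 is a conflict between two stated rules. Step 3 is an ambiguity.

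**The case against.** The strongest reply is that Section G should be read as a whole. It plans examination and telephone contact throughout, introduces monitoring by referring to unanticipated events, names two qualified assessors, and gives them a scale that reaches Unrelated. No sentence tells site staff to apply a causality filter. On that reading, candidate events reach the assessors, who then classify them, and the causal clause is merely poor drafting.

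Much of this stands. The two lowest categories suggest that the authors meant to collect such events, and staff may well do so. But surveillance is for adverse events as defined, and no rule requires an unsuspected event to be passed on. If the intention was to collect everything, the definition should say so.

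A reader might infer more than the documents support:

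- *That infant events caused through milk are excluded.* This does not follow. If drinking the beverage is a study procedure, an infant event arising from it through milk is also caused by a study procedure. The infant meets the other condition through the heel stick.
- *That infants are expected to come to harm.* The effects discussed in Section B are long-term and would not be seen in this study. Section D puts the maternal dose below the acceptable daily intake for both sweeteners.
- *That severe events slip past the seriousness rule.* The threshold is grade 3, so any event recorded as an adverse event and graded severe is already in the serious class.
- *That the loss can be quantified.* Any figure would need an assumed recording share for which the documents give no basis.

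**Conclusion.** The concern holds in a limited form. The definition and the attribution scale describe different sets of recordable events. Read literally, events not suspected at first may be left out of recording, grading, reporting and review, and so may never reach the principal investigator and the neonatologist. Coverage of events attributed to the beverage or to sweetener in milk is unclear; the documents do not show that they are excluded.

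The number of events affected is unknown. Neither aim estimates an event rate, and the pharmacokinetic aims and analyses do not depend on this wording. The conclusion assumes that staff would apply the definition as written and that no separate recording instruction exists outside the documents supplied. Confidence is moderate, because the rest of Section G suggests a wider intention. The change is still worth making: it is inexpensive and it improves the safety record for mothers and infants.

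**What to change.** Reword the definition in Section G so that every untoward medical event in a mother or infant during the study is recorded, whether or not it is thought related to the intervention (including sweetener received through milk) or to study procedures. Each recorded event is then attributed on the existing five-level scale by the assessors already named. The new wording should also say when recording starts, since Section D places enrollment about one week before the in-person visit.

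The cost is an IRB amendment and somewhat more events to record; how many more is unknown. There is one side effect. Under the present threshold, unrelated moderate (grade 3) events would fall in the serious class, although the 24-hour report would apply only if they were also unanticipated. Disability also appears at both grade 4 and grade 5. The sponsor and IRB should reconcile the definition with the severity and seriousness wording in the same amendment. Sampling, sample size and the pharmacokinetic analysis do not change.
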